5.1 KRd+Elotuzumab Induction Regimen

All subjects enrolled will receive KRd+elotuzumab induction. See Section 6 for details on drug administration and dose modifications/delays. **NOTE:** Pre-hydration is required for carfilzomib as described in Section 6.3.2 and premedication is required prior to elotuzumab as described in Section 6.4.1.

Table 1: KRd+Elotuzumab Induction Regimen

Drug	Dose	Route	Schedule	4-Week (28D) Cycle
Carfilzomib ^{a,b}	20 mg/m ²	IV	D1	Cycle 1
Carfilzomib ^{a,b,c}	56 mg/m ²	IV	D8, 15	Cycle 1
Carfilzomib ^{a,b,c}	56 mg/m ²	IV	D1, 8, 15	Cycles 2-4
Lenalidomide	25 mg ^d	Oral	Once a day at bedtime on D1-21	Cycles 1-4
Dexamethasone ^g	28 mg	Oral	Once weekly ^e on D1, 8, 15, 22	Cycles 1-2
	8 mg	IV		
Dexamethasone ^{e,g}	28 mg	Oral	D1	Cycles 3-4
	8 mg	IV		
Dexamethasone ^{f,g}	40 mg	PO	Once weekly on D8, 15 and 22	Cycles 3-4
Elotuzumab ^b	10 mg/kg	IV	Once weekly on D1, 8, 15, 22	Cycles 1-2
Elotuzumab ^b	20 mg/kg	IV	D1	Cycles 3-4

^a Calculate the dose using the subject's actual body surface area (BSA) at baseline. For subjects with a BSA >2.2m², calculate the dose based upon a BSA of 2.2m².

^b If a subject's weight changes by more than 10% from induction cycle 1 day 1 the dose of carfilzomib and elotuzumab should be recalculated. This re-calculated weight should be used as the new baseline weight. **NOTE:** use the subject's actual (not ideal) body weight for dosing as per the American Society of Clinical Oncology (ASCO) guidelines in dosing of obese adult subjects.

^c **NOTE:** In subjects who enroll with a bilirubin and/or AST >1 x ULN, the starting dose of carfilzomib of 20mg/m² should be maintained and not increased to 56mg/m². The dose may be escalated to 56 mg/m² if both bilirubin and AST resolve to ≤ ULN.

^d For subjects who enroll with a CrCl between 40-50 mL/min, the starting dose of lenalidomide may be reduced to 10mg at the discretion of the investigator.

^e On days when elotuzumab is administered: 28mg PO between 3-24 hours prior to start of elotuzumab **OR** as a split dose of 12 mg 12-24 hours and 16 mg 3 hours prior to elotuzumab; 8 mg IV 45 to 90 minutes prior to elotuzumab infusion. **NOTE:** This will serve as the corticosteroid premedication for elotuzumab on days when elotuzumab is administered during induction

^f May administer 20 mg dexamethasone for subjects ≥ 75 years old

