6.3.4.1 Hematologic Toxicities

NOTE: Thrombocytopenia has been transient and typically resolves during the week between treatments.

Table 4: Dose Modifications for Hematologic Toxicities

Toxicity	Recommended Action
ANC < 500/mm ³	
 First occurrence: Hold dose; resume at same dose level once ANC recovers to $\geq 500/\text{mm}^3$ For any recurrence: hold dose; resume with dose reduced by 1 level once ANC recovers to $\geq 500/\text{mm}^3$
ANC < 500/mm ³ and temperature >38.5°C or 2 consecutive readings of >38.0°C for 2 hours	
 Hold dose; resume at same dose level once ANC returns to baseline and fever resolves
Platelets < 10,000/mm ³ or evidence of bleeding with thrombocytopenia	
 First occurrence: Hold dose; resume at same dose level once platelets recover to $\geq 10,000/\text{mm}^3$ and/or bleeding is controlled For any recurrence, hold dose; resume with dose reduced by 1 level once platelets recover to $\geq 10,000/\text{mm}^3$ and/or bleeding is controlled

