6.3.4.2 Non-Hematologic Toxicities

Creatinine clearance (CrCl) changes associated with carfilzomib are mostly transient, reversible, and non-cumulative. Renal function must be monitored closely during treatment with carfilzomib. Serum chemistry values, including creatinine, must be obtained and reviewed prior to each dose of carfilzomib on Day 1, 8, and 15 during induction. Creatinine clearance should be calculated on Day 1 of each cycle.

Carfilzomib treatment can cause nausea, vomiting, diarrhea, or constipation sometimes requiring the use of antiemetics or antidiarrheals. Fluid and electrolyte replacement should be administered as clinically indicated to prevent dehydration.

Subjects with active or suspected infection of any kind that require systemic treatment should not be dosed with carfilzomib until the infection has resolved and if being treated with an anti-infective(s), the course of antibiotics has been completed.

Subjects with a history of HBV should be closely monitored for signs and symptoms of active HBV infection throughout treatment with carfilzomib, including the 30-day safety monitoring follow-up period.

Subjects receiving carfilzomib should be monitored for any new or worsening neurologic, cognitive or behavioral signs and symptoms that may be suggestive of Progressive Multifocal Leukoencephalopathy (PML) as part of the differential diagnosis of central nervous system disorders. If PML is suspected, subjects should be referred to a specialist and appropriate diagnostic testing should be initiated. If a PML diagnosis is confirmed, carfilzomib should be permanently discontinued.

Table 5: Dose Modifications for Non-hematologic Toxicities

Toxicity	Recommended Action
Serum creatinine ≥ 2 X baseline or CrCl < 15 mL/min, or CrCl decreases to $\leq 50\%$ of baseline, or need for hemodialysis (Creatinine clearance only applicable for Day 1 of each cycle)	
 • Hold dose and continue monitoring renal function • If attributable to carfilzomib, resume with dose reduced by 1 level once renal function has recovered to within 25% of baseline • If not attributable to carfilzomib, dosing may be resumed at discretion of investigator • If on hemodialysis, administer the dose after the hemodialysis procedure

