In subjects who enroll with bilirubin and AST $< \text{ULN}$ at baseline, and bilirubin increases to >1 to $3 \times \text{ULN}$ and/or AST increases to $> \text{ULN}$	
 • Hold dose; resume with dose reduced by 1 level once resolved or returned to baseline
In subjects who enroll with bilirubin and/or AST $> \text{ULN}$ at baseline, and bilirubin and/or AST increases by 1 grade	
 • Hold dose; resume with dose reduced by 1 level once resolved or returned to baseline
\geq Grade 3 non-hematologic toxicity ^a	
 • Hold dose; resume with dose reduced by 1 level once resolved or returned to baseline
If Posterior Reversible Encephalopathy Syndrome (PRES) is suspected	
 • Hold dose; consider evaluation with neuroradiological imaging, specifically MRI, for onset of visual or neurological symptoms suggestive of PRES. • If confirmed, permanently discontinue carfilzomib • If the diagnosis of PRES is excluded and if clinically appropriate, restart dose administration • If PRES recurs, permanently discontinue carfilzomib
If thrombotic microangiopathy (TMA) (TTP/HUS) is suspected	
 • Hold dose; and manage per standard of care including plasma exchange as clinically appropriate • If TMA is confirmed and related to carfilzomib, permanently discontinue • If diagnosis is excluded, carfilzomib can be re started at the previous dose • If the condition recurs, permanently discontinue carfilzomib

Hypertensive Urgency/emergency (defined as sustained or persistent SBO \geq 180 mmHg or DBP \geq 110mmHg)	
 Hold dose until resolution to baseline and restart at 1 dose decrement
If Progressive Multifocal Leukoencephalopathy (PML) is suspected	
 Withhold carfilzomib; refer promptly to a specialist; appropriate diagnostic testing should be initiated If a diagnosis of PML is confirmed, permanently discontinue carfilzomib
Active HBV reactivation	
 Withhold carfilzomib until the infection is adequately controlled. If the benefits outweigh the risks, carfilzomib may be resumed with concomitant prophylaxis as per local standard of care. Consult a liver disease specialist as clinically indicated.

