³ The post-induction disease evaluation (blood and urine collection and bone marrow biopsy/aspirate) should occur within 7 days prior to treatment on C1D1 of maintenance. The primary endpoint (VGPR or better post induction) will be assessed at this post-induction disease evaluation. See Section 13.1 for details on efficacy evaluations and note that all response categories (CR, sCR, VGPR, PR, and PD) require 2 consecutive assessments.

⁴ A window of +/- 14 days will be applied to all maintenance study visits (includes treatment and required procedures).

⁵ This visit should occur in subjects 30 days (+/-10 days) after treatment stops for whatever reason (toxicity, progression, or at discretion of the investigator). **NOTE:** subjects who have ongoing Grade 4 AE or SAE at the time of the Safety Follow-up Visit will continue to be followed until the event is resolved or deemed irreversible by the investigator.

⁶ For subjects who discontinue study treatment before relapse or PD, disease evaluations should continue to be performed until relapse or confirmed PD, death, start of a new anticancer treatment, withdrawal of consent to study participation, or end of the study, whichever occurs first. The schedule for disease evaluation should follow the schedule outlined during maintenance. Survival follow-up will occur every 3 months (+/- 30 days) from the last administration of protocol-directed therapy or until death, and may be conducted via telephone. Any second primary malignancies discovered during long-term follow-up will be documented.

⁷ Complete physical exam at screening with evaluation by body system, including height, weight and neurologic exam to detect peripheral neuropathy. Thereafter symptom-directed physical exam (to include weight) only. Subjects should also be monitored for second primary malignancies. If a subject's weight changes by more than 10% from induction C1D1, the dose of carfilzomib and elotuzumab should be re-calculated. This re-calculated weight should be used as the new baseline weight.

⁸ Vital signs (to include temperature, heart rate, blood pressure and respiratory rate) should be recorded at screening, before each elotuzumab infusion, and at the Safety Follow-up Visit.

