8.2.2 Day 1 Cycles 1-4 (unless otherwise noted)

- **Physical Exam:** Symptom-directed physical exam (to include weight). Subjects should also be monitored for second primary malignancies. If a subject's weight changes by more than 10% from induction C1D1, the dose of carfilzomib and elotuzumab should be re-calculated. This re-calculated weight should be used as the new baseline weight. For office visits required during the COVID-19 pandemic, virtual visits will be allowed per investigator discretion starting with Cycle 2 Day 1 induction.
- **Performance Status:** ECOG performance status. For required time-points during the COVID-19 pandemic, performance status may be performed virtually if the office visit is being performed virtually (starting with Cycle 2 Day 1 induction)
- **Vital Signs:** Vital signs should include temperature, heart rate, blood pressure and respiratory rate. Measure prior to elotuzumab infusion.
- **Cardiac Evaluation:** ECG
- **Laboratory Assessments**
 - Serum chemistries: BUN, creatinine, (with calculated creatinine clearance on Day 1 of each cycle), glucose, uric acid, calcium, chloride, phosphorus, potassium, sodium, LDH, albumin, total protein, magnesium, total bilirubin, alkaline phosphatase, AST and ALT. **NOTE:** calcium should also be corrected for albumin.
 - CBCD: complete blood count with differential and platelets
 - Pregnancy test (serum or urine) in FCBP; **NOTE:** if screening pregnancy was done within 24 hours of C1D1 it does not to be repeated on C1D1.
- **Disease Evaluation:**
 - Blood and urine tests: Serum QIg (including IgA, IgM, IgG, IgD, IgE), SPEP, UPEP (24-hr urine sample required), serum and urine immunofixation, and serum FLC. Testing for IgD and IgE will only be performed for subjects with IgD and

IgE-type myeloma. Serum FLC to be performed for subjects with light chain only disease and for subjects where a CR is suspected or maintained. Subjects without measurable urine M-Protein at baseline will not be required to have UPEP or urine immunofixation repeated at subsequent disease assessment time-points, unless clinically indicated.

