8.2.3 Day 8, 15 and 22 Cycles 1-2 (unless otherwise noted)

- **Vital Signs:** Vital signs should include temperature, heart rate, blood pressure and respiratory rate. Measure prior to elotuzumab infusion. Cycles 1-2 only
- **Laboratory Assessments**
 - Serum chemistries: BUN, creatinine, glucose, uric acid, calcium, chloride, phosphorus, potassium, sodium, LDH, albumin, total protein, magnesium, total bilirubin, alkaline phosphatase, AST and ALT. **NOTE:** calcium should also be corrected for albumin.
 - CBCD: complete blood count with differential and platelets
 - Pregnancy test (serum or urine) in FCBP: Cycle 1 only

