- **Hypertension:** Hypertension, including hypertensive crisis and hypertensive emergency, has been observed with carfilzomib. In a randomized, open-label, multicenter trial evaluating carfilzomib in combination with KRd *versus* Rd, the incidence of hypertension events was 17% in the KRd arm *versus* 9% in the Rd arm. In a randomized, open-label, multicenter trial of Kd *versus* Vd, the incidence of hypertension events was 34% in the Kd arm *versus* 11% in the Vd arm. Some of these events have been fatal. Monitor blood pressure regularly in all patients.
- **Venous Thrombosis:** Venous thromboembolic events (including deep venous thrombosis and pulmonary embolism) have been observed with carfilzomib. In a randomized, open-label, multicenter trial evaluating KRd *versus* Rd (with thromboprophylaxis used in both arms), the incidence of venous thromboembolic events in the first 12 cycles was 13% in the KRd arm *versus* 6% in the Rd arm. In a randomized, open-label, multicenter trial of Kd *versus* Vd, the incidence of venous thromboembolic events in months 1–6 was 9% in the Kd arm *versus* 2% in the Vd arm. With carfilzomib monotherapy, the incidence of venous thromboembolic events was 2%.
- **Infusion Reactions:** Infusion reactions including life-threatening reactions, have occurred in patients receiving carfilzomib. Symptoms include fever, chills, arthralgia, myalgia, facial flushing, facial edema, laryngeal edema, vomiting, weakness, shortness of breath, hypotension, syncope, chest tightness, or angina. These reactions can occur immediately following or up to 24 hours after administration of carfilzomib.
- **Hemorrhage:** Fatal or serious cases of hemorrhage have been reported in patients treated with carfilzomib. Hemorrhagic events have included gastrointestinal, pulmonary, and intracranial hemorrhage and epistaxis. The bleeding can be spontaneous, and intracranial hemorrhage has occurred without trauma. Hemorrhage has been reported in patients having either low or normal platelet counts. Hemorrhage has also been reported in patients who were not on antiplatelet therapy or anticoagulation.

- **Thrombocytopenia:** Carfilzomib causes thrombocytopenia with platelet nadirs observed between Day 8 and Day 15 of each 28-day cycle, with recovery to baseline platelet count usually by the start of the next cycle. Thrombocytopenia was reported in approximately 32% of patients in clinical trials with carfilzomib.

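### Vital signs are scheduled with elotuzumab only, so 4 of the 12 planned carfilzomib doses have no scheduled blood pressure or temperature, although a carfilzomib hold rule depends on blood pressure

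*Combined protocol and SAP*

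**What the plan says.** Carfilzomib: Table 1 (Section 5.1) schedules it on D1, D8 and D15 of each of the four induction cycles. Section 6.3.4.2 confirms those days when it requires serum chemistries, which "must be obtained and reviewed prior to each dose of carfilzomib on Day 1, 8, and 15 during induction".

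Elotuzumab: in Cycles 1-2 the Table 1 entry is "Once weekly on D1, 8, 15, 22". In Cycles 3-4 it is D1 only.

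Vital signs: three places give the same schedule.
- The Study Calendar (Section 7) marks D1, D8, D15 and D22 of Cycles 1-2 but only D1 of Cycles 3-4.
- Footnote 8 says that vital signs "should be recorded at screening, before each elotuzumab infusion, and at the Safety Follow-up Visit". It does not mention carfilzomib.
- Section 8.2.2 covers D1 of Cycles 1-4: "Vital signs should include temperature, heart rate, blood pressure and respiratory rate. Measure prior to elotuzumab infusion". Section 8.2.3, whose heading is itself limited to Cycles 1-2, adds for D8, D15 and D22: "Measure prior to elotuzumab infusion. Cycles 1-2 only".

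Rules that use these measurements: Table 5 holds carfilzomib under a row that begins "Hypertensive Urgency/emergency (defined as sustained or persistent", with thresholds of 180 mmHg systolic or 110 mmHg diastolic. Table 4 has a row that combines ANC below 500/mm³ with fever, defined by a single temperature above 38.5°C or "2 consecutive readings of >38.0°C for 2 hours". The hypertension warning in Section 10.2.5 ends: "Monitor blood pressure regularly in all patients".

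**The concern.** From Cycle 3 the two infusion schedules separate. Carfilzomib stays on three days per cycle, elotuzumab moves to one, and the vital signs move with elotuzumab. A site that follows the calendar exactly then gives carfilzomib on D8 and D15 of Cycles 3-4 with blood results in hand but no required blood pressure or temperature. Physical examination is also marked on D1 only, so no other scheduled assessment on those days fills the gap.

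The protocol supplies scheduled data for the laboratory-based carfilzomib rules at every dose, so this looks like an oversight rather than a deliberate reduction. Section 10.2.5 lists hypertension, including crisis and emergency, among the carfilzomib warnings and says that some events were fatal. Raised blood pressure can be without symptoms, so a hold criterion could be met and not seen.

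**Working it through.** The plan states no figure on this point, so there is none to reproduce. The check compares sets of days.

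Inputs are Table 1 for drug days and the Study Calendar, footnote 8 and Sections 8.2.2-8.2.3 for assessments.

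| Induction days | Carfilzomib | Elotuzumab | Vital signs | Chemistries and CBCD |
|---|---|---|---|---|
| Cycles 1-2: D1, D8, D15 | yes | yes | yes | yes |
| Cycles 1-2: D22 | no | yes | yes | yes |
| Cycles 3-4: D1 | yes | yes | yes | yes |
| Cycles 3-4: D8, D15 | **yes** | no | **no** | yes |
| Cycles 3-4: D22 | no | no | no | no |

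Counts per subject:
- Carfilzomib doses: 3 days × 4 cycles = 12.
- Elotuzumab doses: 4 × 2 + 1 × 2 = 10. Vital-sign days: 4 × 2 + 1 × 2 = 10, and they are the same 10 days.
- Carfilzomib doses with no scheduled vital signs: D8 and D15 in each of Cycles 3 and 4 = 2 × 2 = 4; 4/12 = 33%.
- Carfilzomib doses with no scheduled chemistries or CBCD: 0 of 12.
- Upper bound on infusions concerned: 4 × 40 = 160, if all 40 subjects receive every planned dose.

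Hold criteria against scheduled data:
- ANC, platelets, creatinine, bilirubin and AST: scheduled results at 12 of 12 doses.
- Blood pressure (Table 5): a reading on the same day at 12 − 4 = 8 of 12 doses.
- Temperature (Table 4, fever row): also 8 of 12. The effect is smaller, because ANC below 500/mm³ without fever already leads to a hold under the preceding row, and ANC is available at all 12 doses. What temperature decides is which row applies, and the resumption criteria differ: recovery of ANC to at least 500/mm³ in one row, return of ANC to baseline plus resolution of fever in the other.
- Active or suspected infection (Table 5): a clinical judgement with no vital-sign threshold.

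Order of infusion on the 8 shared days: Section 6.3.1 says that carfilzomib is given first when both drugs are due. A reading required only before elotuzumab can therefore be taken after carfilzomib and still comply. So 4 doses have no scheduled reading, and the other 8 have one whose required timing does not place it before carfilzomib.

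**The case against.** The strongest reply is that subjects are in an infusion clinic on these days and vital signs will probably be taken anyway. Section 10.2.5 tells investigators to watch blood pressure, Section 6 leaves every action in the dose-modification tables to the investigator's discretion, and the Table 5 row requires a sustained elevation, which one reading does not establish. An elotuzumab dose delayed within the 14-day limit of Table 9 could also bring vital signs to D8 or D15.

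Part of this stands. The documents do not show that readings would be omitted, only that none is required. But the Section 10.2.5 sentence names no visit, discretion still needs a measurement to act on, a first reading is what prompts a repeat, and a delayed elotuzumab dose is incidental. The restriction to Cycles 1-2 tells sites that later readings are not called for.

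A reader might infer more than the documents support:
- That none of the carfilzomib hold rules can be applied on these days. The laboratory rules can, an ANC below 500/mm³ alone leads to a hold, and suspected infection is judged clinically.
- That the 17% (KRd) or 34% (Kd) hypertension rates in Section 10.2.5, applied to 40 subjects, size the problem. They are trial-wide incidences of any hypertension event, the second from a different regimen, and do not count events missed on four infusion days. The same section gives Grade 3 or higher hypertension in 12 of 392 KRd subjects (3%) over 12 cycles, which does not count them either.
- That the gap leaves carfilzomib infusion reactions undetected. Section 10.2.5 places these immediately after, or up to 24 hours after, administration. Pre-dose readings would not find them.
- That hypertension will be under-counted in Cycles 3-4 relative to Cycles 1-2. Section 8.2.1 records all AEs throughout induction, Section 12.1.6 covers findings from assessments that the protocol does not require, and Section 14.5.6 plans no comparison between cycles.

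**Conclusion.** The mismatch is real, and the calendar row, footnote 8 and Section 8.2.3 show it consistently, so it is not a table-reading artefact. Four of 12 planned carfilzomib doses (33%) have no scheduled blood pressure or temperature, against none of 12 without scheduled laboratory results. The conflict of substance is with the Table 5 blood-pressure row and the Section 10.2.5 instruction; the temperature element of Table 4 is secondary. The timing on shared days is a further, smaller weakness.

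This assumes that the calendar is followed as written, that subjects remain on the planned carfilzomib and elotuzumab days, and that the systolic abbreviation in Table 5, printed as SBO, means systolic blood pressure. How often a hold would be missed cannot be estimated from the documents. The VGPR+ endpoint and its test are not affected. The point is worth correcting because it concerns subject safety and costs little.

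**What to change.** Reconcile these places with the carfilzomib days in Table 1 and the hold criteria in Tables 4 and 5, so that each hold criterion has a scheduled measurement on the dosing days it governs:
- the vital-signs row of the Study Calendar for D8 and D15 of Cycles 3-4;
- footnote 8, which names elotuzumab only;
- Section 8.2.3, both its heading and the Cycles 1-2 restriction on vital signs. Removing the restriction alone would leave the heading's limit, and no part of Section 8.2 lists day-specific procedures for D8 and D15 of Cycles 3-4;
- the stated timing of vital signs on days when both drugs are given, in view of the infusion order in Section 6.3.1.

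The clinical content is for the sponsor to settle. The reconciliation need not alter any dose, threshold or hold rule. The cost is two calendar cells, a footnote, and a revised heading or a short new subsection. For sites it is a few minutes at four visits per subject that are already attended for blood tests and infusion.
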